Patient demographics and clinical characteristics. Patient demographics and past medical history will be collected as part of the study (Appendix D). Patient demographic variables to be collected include age, race, education level, marital status, and employment status. Specific confounding variables associated with the type of intervention and outcome will be collected including patients' preferred learning style, comfort level with technology, and anxiety. Preferred learning style will be assessed using the three styles of learning reading, seeing, doing, or listening (Bastable, 2008). Comfort level with technology will be assessed using a five-point Likert scale with zero being, "not comfortable at all" and five being "very comfortable." Anxiety associated with anticipated pain will be assessed on ten-point. Relevant past medical and surgical history will also be collected including past major orthopedic surgeries, chronic pain, preoperative use of opioids, and mental health conditions. The patient demographic collection form will be administered using paper and pencil survey. The patient will be given the form when they arrive to the ambulatory orthopedic clinic for their perioperative visit, one to two days prior to their scheduled surgery. It will take participants approximately five minutes to complete the survey.

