Pain knowledge. The Patient Pain Questionnaire (PPQ) will be used to evaluate pain knowledge post intervention (Appendix F). The PPQ is a 16-item questionnaire measuring both pain knowledge and actual experiences with pain. This study will use only nine of the items targeted at pain knowledge and beliefs. The nine knowledge-based questions use a ten-point (0-10) ordinal scale to assess patients' agreement or disagreement with statements about pain relief, medication administration, addiction, dosing, timing, non-pharmacologic management, side effects, beliefs about pain medications, and changes in the pain experience. Depending on the statement a higher score may indicate either agreement or disagreement with the statement. All items have been formatted so that zero indicates the most positive outcome and a ten indicates the most negative outcome. These nine items are primarily used for chronic cancer pain; however the PPQ has been and can be adapted to assess general pain knowledge and experiences. Psychometric analysis of the PPQ demonstrated content validity of 0.90 (content validity index), construct validity of <0.05 variance, concurrent validity ($r=0.60$; $p <0.05$), test-retest reliability ($r=0.80$), and internal consistency with a Cronbach α of 0.71 (Ferrel & Rivera, 1997). The language will also be revised, as in the study conducted by Reynolds (2009) and reference to chronic cancer pain will be removed from the original question. This tool is open source and available for application without further permission and may be utilized by clinicians or researchers (City of Hope Pain and Palliative Care Resource Center, 2017; MIDSS, n.d.).

At the start of the study and at the time of discharge the patient will complete the APS-POQ-R and the revised knowledge-based PPQ surveys. It will take participants approximately 10 minutes to complete the two surveys. The use of these two widely used instruments will ensure that the information being collected is highly reliable and valid, truly measuring what the study is seeking to evaluate. These paper and pencil surveys will be provided to the patient prior to discharge and collected from the patient by the staff registered nurse (RN) and/or charge nurse. In addition to training and education on the intervention, staff will receive direction on the data (survey) collection process and requirements.

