Chart audits. Chart audits of the electronic health record will be conducted after discharge to collect the remaining clinical data. Data to be collected will include total opioid requirements as indicated by the medication administration record; primary surgical procedure as reported in the surgical listing and the operative report; type of regional anesthesia as indicated in the anesthesia record; length of stay; and discharge disposition as reported in the hospital dismissal summary. Additionally, the past medical history will be reviewed to confirm patient reported history of chronic pain, preoperative use of opioids, and mental health conditions. The researcher and a staff RN will conduct these chart audits.

Limitations

The design of this study does present some limitations. Participants in the study group will receive enhanced pain content that is delivered using an alternative method, ultimately testing both the delivery method and the content. The duality of the study intervention is a confounding variable and may make differentiating

the cause of the outcome difficult. Another limitation is that preoperative educational classes are available to patients to attend if they choose. All patients receive the same pamphlets and information in the mail when surgery is scheduled. An in-person didactic class is optional for patients. Some pain education is offered in this class. Currently only 49% of patients attend these classes. It is anticipated that some patients enrolled in the study will have received varying levels of education prior to their hospital admission. This is an antecedent variable that will be collected as part of the chart audit and accounted in the data analysis. The two nursing units involved in the study are located within the same hospital. It is possible that nursing staff from the intervention unit may float to the control unit and educate study patients using content from the expanded education from the intervention on the iPads. Pre-testing knowledge of pain and measured again at the end of the intervention (prepost) using a paired t-test analysis will strengthen the design of the study. Only opioid use for pain control is being measured.

Data Management

Data Collection Procedure

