Data will be collected at three points in time using paper and pencil survey's and chart audits. The data collection protocol can be found in Appendix G. After completion of the HIPAA form, demographic and past medical history information and pain knowledge survey will be administered in the ambulatory clinic at the time of the perioperative surgical visit. A paper and pencil survey/form will be provided to the patient when they arrive in the clinic for their perioperative appointment and returned to the desk staff when completed.

The intervention will occur on the postoperative inpatient care unit (PCU) starting at the time the patient arrives on the unit from the post anesthesia care unit (PACU). The intervention will continue through the course of care until discharge. At the time of discharge the patient will complete the Revised American Pain Society Patient Outcomes Questionnaire (APS-POQ-R) (Gordon et al., 2010) and the revised knowledge-based Patient Pain Questionnaire (PPQ) (Ferrell & Rivera, 1997; Reynolds, 2009). The use of these two widely used instruments will ensure that the information being collected is highly reliable and valid, truly measuring what the study is seeking to evaluate. These paper and pencil survey's will be provided to the patient prior to discharge and collected from the patient by the staff registered nurse (RN) and/or charge nurse. In addition to training and education on the intervention, staff will receive direction on the data (survey) collection process and requirements. The administration of the post-intervention surveys at the point of care, before the patient has left the study environment, will help to prevent the loss of study participants due to non-response or failure to complete follow-up surveys.

After discharge the researcher will conduct a chart review to collect clinical data including opioid consumption totals, past medical history, anesthesia type, and length of stay. The researcher in addition to one RN will be responsible for chart audit data collection. The RNs will be trained by the researcher on chart audit processes. The RNs will complete the institutions IRB education requirements for staff assisting with research data. A tentative timeline has been developed as a GNATT chart in Appendix H. All collected data from the paper surveys' and chart audits will be entered in to SPSS for analysis. Data storage and management is discussed further under ethical considerations.

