Account, member, certificate or professional license numbers, health beneficiary numbers		
Vehicle identifiers and serial numbers, including license plate numbers		
Check 'None' when none of the identifiers listed above will be recorded, maintained, or shared during the conduct of this study. (exempt category 4)	 None	 None

Data Analysis

Power analyses and study endpoints are not required for minimal risk research, pilot or feasibility studies.

No statistical information. *If checked, please explain:*

Power Statement: N/A

Data Analysis Plan

The pre-intervention and post-intervention, paper surveys' will be returned to the researcher for data entry and storage. The collected data will be collated and entered by the researcher into SPSS for data analysis. A detailed code book has been developed to include specific information on the type of variable and the theoretical and operational definitions. Data entry will be double-checked for accuracy by one of the staff trained staff RNs participating in data collection and chart audits. Descriptive statistics will be performed on each study variable. Continuous variables, including pain scores, pain knowledge, and opioid requirements, will be reported using a mean and standard deviation. Categorical variables, including patient characteristics and education engagement, will be reported as frequencies and percent occurrence. The data will be examined for any baseline differences between the groups to identify characteristics that may confound results and require control in the analysis. Data will be examined to assure that it meets the assumptions of normality required for parametric analysis. If data does not meet normality assumptions, nonparametric analyses will be used. This study uses a revised adaption of the Patient Pain Questionnaire (PPQ) survey. For this reason, the reliability and validity of the nine knowledge based questions will be evaluated using Cronbach's alpha and factor analysis.

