This study will explore the difference between two types of education delivery methods and the effect on pain scores, participation, knowledge, and opioid requirements. The difference amongst the two study groups will be analyzed using an independent *t*-test. Using the population mean of each group a *t* statistic will be computed. The independent *t*-test was selected because this statistical test is appropriate when there are two groups that are not the same people and are not connected to one another in any other systematic way (Polit, 2010). Additionally, the requirements for the *t*-test fit with the design of the study and variables. The independent variable must be dichotomous nominal level indicating a participants' status in one of the two groups and the dependent variable must maintain the characteristics of interval-scale or ratio (Polit, 2010).

Endpoints

Primary: N/A

Secondary: N/A

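### The only between-arm test named takes no covariates: the foreseen confounder control has no stated method, and baseline knowledge has no stated role in comparing the arms

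*Combined protocol and SAP*

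**What the plan says.** **Between-arm test.** The Data Analysis Plan covers pain scores, participation, knowledge and opioid requirements with one sentence: "The difference amongst the two study groups will be analyzed using an independent" *t*-test. It does not say whether discharge scores or changes from baseline enter the test. The fallback is "If data does not meet normality assumptions, nonparametric analyses will be used", with no test named.

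**Confounder control.** The same section says the data will be "examined for any baseline differences between the groups to identify characteristics that may confound results and require control in the analysis". Limitations says of attendance at the optional preoperative class: "This is an antecedent variable that will be collected as part of the chart audit and accounted in the data analysis". Instruments says: "Specific confounding variables associated with the type of intervention and outcome will be collected", and lists learning style, comfort with technology and anxiety. No regression, ANCOVA, stratification, matching or weighting is named.

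**Baseline knowledge.** Instruments says: "At the start of the study and at the time of discharge the patient will complete the APS-POQ-R and the revised knowledge-based PPQ surveys". Data Collection Procedure agrees for the PPQ: the "pain knowledge survey will be administered in the ambulatory clinic at the time of the perioperative surgical visit". The only analysis given for the pair of knowledge scores is in Limitations, where knowledge pre-tested and "measured again at the end of the intervention (prepost) using a paired t-test analysis will strengthen the design of the study".

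**Allocation.** The Design section calls the study quasi-experimental. The arm follows the unit where the patient is bedded. Patients are said to reach a unit by chance and bed availability, the iPad unit is itself picked at random, bed control is asked only for an even split, and the researchers do not know the arm until a bed is assigned. No patient-level random sequence is described.

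**The concern.** A two-sample t-test has no place for a covariate, so the one analysis named for comparing the arms cannot by itself carry out the control that the plan foresees. The model and the covariates are left open, to be settled after baseline data have been examined and possibly after outcomes are known. Different reasonable choices could then give different answers.

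The paired t-test does not fill the gap for knowledge. It compares patients with themselves, and both arms may improve, so it says nothing about which form of education did better. Two things are at stake. If the two units' patients differ at baseline, a discharge-only comparison carries part or all of that difference into the result. And if discharge scores alone are compared, the precision offered by a baseline score already being collected is lost.

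**Working it through.** **Inputs.** From Sample Size: d = 0.50, power 0.80, alpha 0.05, 64 per arm. Two-sided testing is inferred, because it reproduces the stated number. The pre-post correlation *r* of the nine reworded PPQ items is not in the documents; I assume 0.2, 0.4 and 0.6. A systematic baseline gap *g* between the units' patients is also assumed, at 0.1, 0.2 and 0.3 SD. SDs are set to 1 and taken as equal at both times. √(n/2) = √32 = 5.657.

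**1. The plan's own figure.** The exact two-sided t-test calculation gives 63.77, so 64 per arm, with power 0.801. The one-sided version gives 51. The stated 64 is thus the size for a test without covariates.

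**2. Power for knowledge at 64 per arm.** Noncentrality is the standardised effect times 5.657.
- Discharge-only t-test: effect 0.50.
- ANCOVA: effect 0.50/√(1 − r²), 125 df. For r = 0.2: 0.50/0.980 = 0.510, and 0.510 × 5.657 = 2.887.
- Change-score t-test: effect 0.50/√(2(1 − r)).

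| r | Discharge t-test | ANCOVA | Change score |
|---|---|---|---|
| 0.2 | 0.801 | 0.817 | 0.602 |
| 0.4 | 0.801 | 0.865 | 0.727 |
| 0.6 | 0.801 | 0.939 | 0.881 |

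**3. False positives of a discharge-only t-test with no true effect.** If the gap regresses to a common mean, the bias is r × g. If it persists in full, the bias is g. Noncentrality is the bias times 5.657, with 126 df. For g = 0.3 persisting, that is 1.697.

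| Gap (SD) | Regresses: r = 0.2, 0.4, 0.6 | Persists |
|---|---|---|
| 0.1 | 5%, 6%, 6% | 9% |
| 0.2 | 6%, 7%, 10% | 20% |
| 0.3 | 6%, 10%, 17% | 39% |

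Averaged over chance imbalance alone, the rate is 5% for the t-test, ANCOVA and change score alike.

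**4. The alternatives under the same 0.3 SD gap** (simulation, 40,000 runs per cell; r = 0.2, 0.4, 0.6).
- Gap regresses: ANCOVA 5% throughout; change score 19%, 15%, 12%, from a bias of −0.3(1 − r) = −0.24, −0.18, −0.12 SD.
- Gap persists: ANCOVA 27%, 19%, 13%, from a bias of 0.3(1 − r) = 0.24, 0.18, 0.12 SD; change score 5%.

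ANCOVA and change score are each unbiased in one case. ANCOVA is less biased than the discharge-only t-test in both.

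**5. Price of covariates that explain nothing.** The variance factor is 125/(125 − k) for k covariate df.
- k = 7: 125/118 = 1.059; noncentrality 2.828/√1.059 = 2.748; 119 df; power 0.778. The covariates break even at about 6% of outcome variance.
- k = 12 (six 1-df covariates, plus the seven listed procedure types at 6 df): 125/113 = 1.106; noncentrality 2.689; 114 df; power 0.760; break-even about 10%.
- k = 7, dropping an assumed 5% or 10% of patients for a missing covariate: power 0.755 or 0.731.

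**The case against.** Five points can be made for the plan.

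*The plan already foresees control.* A reader might infer that the plan is unable to adjust for confounders. The documents do not support that: the method is unspecified, not excluded. It is also unfair to say that the screening ignores links to outcome, since the Data Analysis Plan looks for characteristics that may confound. What stands is that no method is stated and the one test named is not such a method.

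*Allocation has safeguards.* A reader might infer that the units' patients do differ, or that patients were steered to an arm. Nothing shows either. Chance and bed availability, a random choice of unit and late unblinding all reduce the risk, and the 39% figure depends on an assumed gap that persists in full. What stands is that bed availability is not a patient-level random sequence and that the plan itself expects to look for imbalance.

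*Baseline may be used after all.* A reader might infer that baseline PPQ is wasted. But an independent t-test on change scores fits the wording and would use it. The supportable point is ambiguity. It matters because, at r = 0.2 or 0.4, the change-score test has less power than the 0.80 planned.

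*ANCOVA is partly a preference.* With non-random groups this is fair, and it is why a change-score sensitivity analysis belongs beside it.

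*The missing detail may lie elsewhere, or not be required.* Appendix B and the code book were not available to me and could hold a covariate list, though they are described as listing variables and definitions, not methods. The template waives power analyses and endpoints for minimal-risk research. It does not supply a method for control that this plan says it will apply.

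**Conclusion.** The concern holds as a gap in specification. The single between-arm test named takes no covariates, the adjustment the plan foresees has no method, and baseline knowledge has no stated part in comparing the arms. This rests on the text and on no assumed figure.

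The size of the consequence does rest on assumptions. Relative to a discharge-only t-test, ANCOVA adds about 2 to 14 points of power for r between 0.2 and 0.6. The harm from bias ranges from none, under chance imbalance, to large, if a 0.3 SD gap exists and persists; the documents do not show which applies. The change is worth making because it is close to free. It is not a sign that the comparison is already biased.

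**What to change.** **Knowledge.** Replace the t-test with a linear model (ANCOVA) of discharge PPQ on arm and baseline PPQ. Keep the paired t-test as description within each arm. Pre-specify the between-arm change-score comparison as a sensitivity analysis, and say that the two methods rest on different assumptions about how a baseline gap behaves.

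**Other outcomes.** Fit a linear model on arm with a short covariate list fixed before outcome data are seen. Draw it from variables the protocol already names, including class attendance; anxiety, comfort with technology, preoperative opioid use, chronic pain, procedure and age are candidates. The exact list is the investigator's choice.

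**Limit to report.** With one unit per arm, patient covariates cannot remove confounding by the unit itself, such as differences in nursing practice.

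**Cost.** Plan wording and one regression per outcome in SPSS, which is already named; no new patients or visits. If the covariates explained nothing, power would fall from 0.80 to about 0.78 with 7 df (procedure collapsed to 1 df) or about 0.76 with 12 df (procedure coded in full). It would be lower still if patients with missing covariates were dropped, so the plan should also say how those are handled.

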
Study Design and Methods

Methods: *Describe, in detail, the research activities that will be conducted under this protocol:*

Variables

The independent variable is the type of patient education deliverable given to the two study arms, group A (experimental group, real-time, interactive, mobile education system) and group B (control group, standard of care). The dependent variables are 1) patient knowledge, 2) patient perceived participation in pain management, 3) high and low pain scores, and 4) total opioid consumption. A simple table of the independent, dependent, and additional variables are presented in Appendix B. A detailed accounting of all data points including variable type, theoretical definitions, and operational definitions can be found in the detailed code book.

Method

Design

This prospective study has been designed as quasi-experimental study. This study design was selected for several reasons. This study seeks to explore both a treatment and control group in efforts to compare outcomes which are dependent on the type of intervention. To control for fidelity of the intervention and avoid cross over, behavior changes from nurses providing the intervention, the intervention the patient receives will be determined by the location they are bedded in hospital. Orthopedic TJA patients are assigned at random and based on bed availability to one of two patient care units. One of the two patient care units will offer standard education the other unit will offer the mobile, iPad based education. The patient care unit to offer the mobile, iPad based education will be selected at random. This study design will help minimize will reduce the risk of selection bias, increase fidelity of the intervention, and increases the probability that the differences demonstrated between the study groups will be attributed to the actual intervention under study.

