The target population is adult patients undergoing elective, lower extremity total joint arthroplasty (TJA). Candidates for inclusion are adult patients over the age of 18 years undergoing surgical intervention and inpatient care for one of the following procedures, total hip arthroplasty (THA) (primary, bilateral, and revision) and total knee arthroplasty (TKA) (primary, bilateral, unicompartmental, and revision). Patients must be fluent in the English language. Patients will be excluded if they are undergoing more complex hip and knee procedures such as implant resections with or without spacer placement, liner exchange, or THA or unipolar hip arthroplasty related to repair of hip fracture. Patients will also be excluded if there are preexisting physical or cognitive limitations that would hinder their ability to use the mobile application.

Sample Size

Assuming a moderate effect size 0.50 (Cohen's d), a power of 80% (0.80), and an alpha of 0.05, 64 participants are needed in each study arm (Polit, 2010). Due to limited time scope, a minimum of 150 patients will be approached for potential participation. If time allows and additional subjects are needed to achieve the desired sample size, additional candidates will be approached to reach the recommended total of 128 patients, divided between the two study arms.

Recruitment and Consent

Eligible patients will be identified using surgeon referral and/or electronic surgical listing reports. Enrollment into the study is completely voluntary. Patients will be recruited at the time of perioperative phone consultation with nursing. This consultation occurs approximately two weeks prior to their scheduled surgical procedure. At this time patients will be introduced to the study by the RN or APRN. If the patient expresses interest, verbal consent will be obtained and documented at the time of the call by the IRB approved consent designees. Consent designees will read the consent script and provide any necessary time to answer the patients' questions. At the time of consent, patients will be informed that there are two study arms and that some subjects will receive enhanced pain management education; however, subjects will not explicitly be informed if they are in the intervention or control arm of the study.

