Patients enrolled in the study arm will be given an iPad on admission to the post-surgical unit. The RN will instruct the patient on how to use the iPad and the program. The device will remain with the patient until discharge. The patient, independently or with the nurse, may use the program at any point during the inpatient care experience. The RN will use the iPad to engage patients in their pain management and care. Intervention fidelity will be monitored by requiring the RN to indicate when and how often they observed and/or directly engaged the patient in pain education using the mobile device. A checklist will be available on the patients chart for the RN to complete at the end of each shift through the duration of the patients hospital stay.

Control group. The control group will receive the current standard of care which consists of verbal instruction and pain management pamphlets. At a minimum, the patients will receive two educational pamphlets titled *Your Pain and Discomfort Management Menu* and *Communicating About Your Pain*. The pain management menu is designed to provide the patient with basic pain information with a focus on non-pharmacologic pain interventions. The pain communication pamphlet offers a more comprehensive explanation about pain, assessment of pain (0-10 scale), communicating with the healthcare providers, and pain management options. The content of these two documents is a portion of the education the study patients will receive using the mobile application. These two documents are existing educational material available through the Department of Patient Education. These educational materials were developed by the Department of Anesthesia and Pain Service in conjunction with the Department of Patient Education. Verbal instruction is inconsistent and is nurse dependent. At a minimum the nurse is instructed to provide the two pamphlets to the patient and follow-up with the patient to address any questions. Additional printed education materials are available through the department of patient education and verbal instruction may be tailored based on nursing assessment and patient need. It is important to note that all educational content available to the study participants is available to the control group in different forms or functions. Fidelity to standard of care will be

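### For inference about the education method, the stated alpha of 0.05 and 80% power hold only if between-unit variance is zero: each arm is one care unit, but the test and the sample size assume independent patients

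*Combined protocol and SAP*

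**What the plan says.** Under Study Design and Methods, Design, there are two orthopedic units. One is picked at random to offer the iPad education and the other gives standard education, so "the intervention the patient receives will be determined by the location they are bedded in hospital". Under Intervention, the unit's nurses use the iPad with patients in one arm and give the pamphlets and verbal teaching in the other. Of the verbal teaching in the control arm the protocol says: "Verbal instruction is inconsistent and is nurse dependent".

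Sample Size takes a Cohen's d of 0.50 and states: "a power of 80% (0.80), and an alpha of 0.05, 64 participants are needed in each study arm". It includes no ICC or design effect.

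The Data Analysis Plan compares the arms with an independent t-test, described as appropriate for "two groups that are not the same people and are not connected to one another in any other systematic way". The only adjustment foreseen is for baseline characteristics that differ between the groups. Limitations lists the mix of content and delivery, the optional preoperative class and floating nurses. It mentions neither clustering nor the fact that each arm is a single unit.

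**The concern.** Patients on one unit share nurses, routines and the staff who hand out and collect the surveys. If this makes their outcomes even slightly alike, the difference between arm means carries a between-unit component as well as patient-to-patient variation. The t-test estimates its standard error from variation within each arm, so it contains none of the between-unit part.

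The hypothesis is about an education method, not about two particular wards. For that question p-values would be too small and intervals too narrow, and a chance difference between wards could be reported at p < 0.05 as an effect of the education.

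**Working it through.** **Inputs.** From Sample Size: d = 0.50 (so SD = 1), alpha 0.05, power 80%, 64 per arm. From Design: one unit per arm. Two-sided testing is not stated, but it is needed to reproduce the 64. The ICC (ρ, the share of outcome variance lying between units) is not in the documents; 0.001 to 0.05 is assumed.

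**1. Reproduce the plan's figure.** With 64 per arm there are 126 degrees of freedom and the noncentrality is 0.5 × √(64/2) = 2.83. Exact two-sided power is 80.1% (79.5% at 63 per arm). The normal approximation gives 63 per arm; a one-sided test gives 50. The 64 is thus the answer for independent patients, with no allowance for clustering.

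**2. Compare the two variances.**
- True variance of the difference: 2[ρ + (1−ρ)/64] = (2/64)(1 + 63ρ).
- Variance the t-test estimates: (2/64)(1−ρ).
- Ratio of true to computed standard error: √[(1 + 63ρ)/(1−ρ)]. At ρ = 0.01 this is √(1.63/0.99) = 1.28.

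**3. Type I error of the planned test.** This is the two-sided tail of t with 126 df beyond 1.979 divided by that ratio. At ρ = 0.01, 1.979/1.283 = 1.54, giving about 12.6%. A simulation of 400,000 draws agrees to within 0.2 percentage points at each ICC.

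**4. Power of a correctly sized test**, with between-unit variance taken as known: Φ(0.5/SE − 1.96), where SE = √[(2/64)(1 + 63ρ)]. At ρ = 0.01, SE = 0.2257, so Φ(2.215 − 1.96) = Φ(0.255) = 60%.

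**5. True 95% half-width:** 1.96 × SE. As the t-test would compute it, 1.96 × √[2(1−ρ)/64] is 0.34 to 0.35 SD throughout.

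| Assumed ICC | Design effect 1 + 63ρ | SE ratio | Type I error | Power, correct size | True half-width (SD) |
|---|---|---|---|---|---|
| 0 | 1.00 | 1.00 | 5.0% | 80% (exact t) | 0.35 |
| 0.001 | 1.06 | 1.03 | 5.7% | 78% | 0.36 |
| 0.005 | 1.32 | 1.15 | 8.8% | 69% | 0.40 |
| 0.01 | 1.63 | 1.28 | 12.6% | 60% | 0.44 |
| 0.02 | 2.26 | 1.52 | 19.5% | 47% | 0.52 |
| 0.05 | 4.15 | 2.09 | 34.6% | 28% | 0.71 |

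**6. ICC at which significance is lost.** An observed d of 0.50 gives t = 0.5 × √32 = 2.828. Setting (2.828/1.979)² = 2.04 equal to 1 + 64ρ/(1−ρ) gives ρ ≈ 0.016.

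**7. Would more patients help?** With one unit of m patients per arm, the effective number is m/[1 + (m−1)ρ], which never exceeds 1/ρ. An effective 64 needs 64(1−ρ)/(1−64ρ) patients per arm: about 94 at ρ = 0.005 and 176 at ρ = 0.01. From ρ = 1/64 = 0.0156 upward, no number suffices.

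**The case against.** **The sentence about unconnected groups is not false.** A reader might infer that the plan contradicts itself, since patients in an arm share a ward. The documents do not support that. The sentence says the two groups are different people and not linked to each other, and sharing a ward within an arm does not conflict with it. The fault is an omission: within-arm independence is never addressed.

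**The ICC could be very small.** Both units are orthopedic wards in one hospital (Setting), nurses may float between them (Limitations), and pain treatment is unchanged in both arms (Recruitment and Consent). The direct evidence of shared influence is at nurse level. That alone has little effect: for an assumed 2 to 5 patients per nurse and ICC 0.02 to 0.05, the design effect is 1 + 1 × 0.02 = 1.02 to 1 + 4 × 0.05 = 1.20. This stands. A reader might infer that false positives will run well above 5%, but at ICC 0.001 the figure is only 5.7%. The statement must stay conditional on the ICC.

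**Patients are said to reach the units at random.** If so, the t-test is valid for comparing these two units. It still does not give the uncertainty of a statement about the education method, because shared unit effects arise after the bed is assigned.

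**This is a minimal-risk, quasi-experimental study with its Power Statement marked N/A.** True, but Sample Size states power and alpha, and Target accrual uses the resulting total of 128. The type I error question does not depend on whether a power statement is required.

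**Power barely falls.** The planned t-test would still reject at d = 0.50 in about 77/75/72/68% of trials at ICC 0.005/0.01/0.02/0.05, and a reader might take this as the power. It is not power at alpha 0.05, because the same test rejects in 8.8 to 34.6% of trials when there is no effect. The figures to quote are 69/60/47/28%.

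**Conclusion.** The concern holds in conditional form. Both the sample size and the t-test assume independent patients within an arm, while the design puts each arm in one unit. For inference about the education method, alpha 0.05 and 80% power are correct only at an ICC of zero. Any positive ICC raises the type I error and lowers the power of a correctly sized test.

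How far they move is unknown. The loss is minor at ICC 0.001 and serious at 0.01 and above. These figures rest on assumed ICCs, exactly 64 patients per unit, two-sided testing and, for power and half-widths, between-unit variance taken as known. In this design it cannot be estimated: one unit per arm leaves zero degrees of freedom between units.

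**What to change.** - **Sample Size:** state that 80% power and alpha 0.05 assume an ICC of zero. Give the correctly sized power, about 78/69/60/47/28% for ICC 0.001/0.005/0.01/0.02/0.05, and say that these ICCs are assumed.
- **Data Analysis Plan:** keep the t-test, but state that its p-values and intervals reflect patient-to-patient variation only and strictly compare these two units. Beside each between-arm estimate, report intervals inflated for ICC 0.001 to 0.05 and the ICC at which significance is lost.
- **Limitations:** state that unit and intervention effects cannot be separated with one unit per arm, and that neither a mixed model nor a cluster-robust standard error can repair this.

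The cost is revised wording and a short sensitivity table, with no extra patients or data. The downside is wider intervals and a less favourable stated power. These changes make the uncertainty visible but do not remove it. Removing it would take a different design, such as several units per arm, units crossing over between conditions, or individual randomisation within units.
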